Objectives	
1) To determine if 5 doses of Epo 1000 U/kg (birth weight) intravenous (IV) reduces the rate of death or neurodevelopmental impairment (mild, moderate, or severe) at 24 months of age.
 
2) To assess safety of Epo.
 
3) To determine whether Epo decreases the severity of HIE-induced brain injury as evidenced by early MRI and plasma biomarkers of brain injury.

Design	Prospective, randomized, double-masked, placebo-controlled study
Arms	
Treatment: Hypothermia (standard of care) plus Epo
 
Placebo: Hypothermia (standard of care) plus normal saline

Procedures	
 - Screen all cooled infants to evaluate eligibility for HEAL - Determine severity of encephalopathy using modified Sarnat exam - Consent and randomize patients - Randomized subjects receive five doses of either study drug or placebo - First dose administered within 24+2 hours of age (Study Day 1); subsequent doses given at the same time of day on Study Days 2, 3, 4, and 7 - Brain MRI and MR spectroscopy ideally performed between 96 and 144 hours post-birth, as part of routine clinical care - Blood collected prior to administration of first study drug dose, and on Study Days 2 and 4 (3 samples total, 1.5 mL each) - Urine (2 samples) collected on Study Days 0-1, and after completion of rewarming on Study Days 3-4 - Phone follow-up at 4, 8, 12, 18, and 24 months: parental questionnaires regarding intervening medical and developmental history, and developmental milestones (Warner Initial Developmental Evaluation of Adaptive and Functional Skills (WIDEA), 12, 18, and 24 months only); All phone interviews may be done in person if desired - 24-month in-clinic evaluation includes a standardized neurologic exam, Bayley III, Gross Motor Function Classification System (GMFCS) evaluation, Child Behavior Checklist (CBCL), and growth parameters. For extenuating circumstances, for example, COVID-19 restrictions, the in-person elements of the final endpoint evaluation may be performed up to 36 months of age. - Extended contact phone calls every 6 months from 2.5 through 8 years of age (WIDEA at 30 and 36 months)
Sites	At least 15, and up to 30 centers in the United States

TABLE OF CONTENTS

SYNOPSIS.....	8
1 STUDY OBJECTIVES	9
1.1 SPECIFIC AIMS.....	9
1.1.1 Aim 1: Efficacy	9
1.1.2 Aim 2: Safety	9
1.1.3 AIM 3: Biomarkers of Neonatal Brain Injury	10
1.2 ENDPOINTS.....	10
1.3 OVERVIEW OF STUDY DESIGN	10

11	HUMAN SUBJECTS	60
11.1	INSTITUTIONAL REVIEW BOARD REVIEW AND INFORMED CONSENT	60
11.2	SUBJECT CONFIDENTIALITY	60
11.3	STUDY MODIFICATION/DISCONTINUATION	60
12	PUBLICATION OF RESEARCH FINDINGS	61
13	REFERENCES	62
14	APPENDICES	71
14.1	ACRONYMS	71

SYNOPSIS

Hypoxic-ischemic encephalopathy (HIE) is a significant cause of neonatal encephalopathy. Although neonatal infection, stroke, and metabolic abnormalities can also cause NE, HIE accounts for about 60% of cases.¹ The incidence of HIE ranges from 1-7 per 1000 births in developed countries, depending on the definition used, with most estimates ranging between 1-3 per 1000. An estimated 12,000 infants are affected each year in the US.²

Neonatal HIE accounts for 22% of annual neonatal deaths worldwide, totaling 814,000 deaths in 2008.² HIE is unpreventable in most cases, and therapies are limited. Hypothermia initiated within 6 hours improves outcome,³⁻⁷ yet despite this therapy 44-53% of infants with HIE die or suffer moderate to severe disabilities including cerebral palsy (CP), intellectual disability, epilepsy, and visual impairment. When a normally developing fetus suffers brain injury leading to lifelong neurologic disability, there is excruciating heartbreak for all involved. Each year, infants who develop CP as a consequence of neonatal HIE will impose an economic burden of \$1.7 billion in their lifetime medical and non-medical costs in the U.S. This figure does not include the costs incurred by children with cognitive impairment, epilepsy, visual impairment and other adverse neurodevelopmental outcomes due to HIE. Additional neuroprotective therapies are urgently needed.

The hematopoietic cytokine erythropoietin (Epo) has remarkable neuroprotective and neuroregenerative effects in the brain in animal models of neonatal brain injury.⁸⁻¹³ Over 70 pre-clinical studies have tested the neuroprotective effects of Epo following hypoxic-ischemic brain injury, and these have produced impressive histologic and functional evidence for benefit ranging from 40 to 78% improvement in infarct size.^{11,14-20} In non-human primates, Epo reduces the rate of CP and improves neurologic function in animals undergoing hypothermia for HIE.²¹

Two clinical trials suggested that infants with HIE treated with 5-7 doses of Epo experienced improved neurologic outcomes compared to infants who received placebo.^{22,23} In a pilot phase I study, we found that Epo was safe, exhibited desirable pharmacokinetics, and resulted in a surprisingly low rate of moderate/severe disability even among infants with significant brain injury seen on MRI.²⁴ In a phase II study, we found that infants randomized to receive multiple doses of Epo had less brain injury on MRI and better 12-month motor outcomes than those who received placebo.²⁵ Given the compelling preclinical data, the suggestive findings from human trials, the favorable safety and pharmacokinetic data, and the unacceptable rate of adverse long-term neurologic outcomes in HIE, we will now perform a phase III trial to determine whether high-dose Epo improves neurodevelopmental outcomes following HIE.

1 Study Objectives

We hypothesize that high-dose Epo given to cooled infants with moderate/severe HIE will reduce the primary outcome of death or neurodevelopmental impairment (mild, moderate or severe) at 24 months of age from 49% to 33% or less. We further hypothesize that neonatal Epo will be safe, will decrease brain injury severity on neonatal MRI, and will decrease serial inflammatory cytokines and biomarkers of brain injury. We expect this finding will change clinical practice. In a randomized, double-masked, placebo-controlled efficacy trial of 500 infants with HIE, we have **three specific aims**, which will be evaluated by the endpoints detailed below:

- Aim 1: Efficacy
- Aim 2: Safety
- Aim 3: Biomarkers of neonatal brain injury

1.1 SPECIFIC AIMS

1.1.1 Aim 1: Efficacy

To determine whether Epo therapy (1000 U/kg (birth weight) given intravenously (IV) on Study Days 1, 2, 3, 4, and 7) reduces the composite primary outcome of death or neurodevelopmental impairment at 24 months of age. Since death is a competing outcome, it is critical to include it in the primary outcome measure.

Neurodevelopmental impairment (mild, moderate, or severe) is defined as any of the following:

- Gross Motor Function Classification System (GMFCS) level ≥ 1 , or
- GMFCS = 0 or 0.5 AND CP (any type), or
- Bayley Scales of Infant and Toddler Development 3rd Edition (Bayley III) Cognitive Score <90

Secondary analyses: we will examine the effect of Epo on CP, severity of motor impairment, Bayley III cognitive and language scores, epilepsy, and behavioral abnormalities. We will also evaluate how Epo shifts the distribution of outcomes by evaluating a 4-level outcome measure: 1) normal; 2) mild motor and/or cognitive impairment; 3) moderate/severe motor and/or cognitive impairment; and 4) death.

Overall severity will consist of the *worst* severity observed in either motor or cognitive outcomes. Severity of motor impairment is defined by type of CP and GMFCS level. Severity of cognitive impairment is determined by Bayley III cognitive score, where Severity is defined as:

- Severe: <70
- Moderate 70-84
- Mild: 85-89
- None: ≥ 90

1.1.2 Aim 2: Safety

To establish the safety of high dose Epo treatment in the setting of HIE and hypothermia, by comparing Epo-related safety measures in infants treated with Epo vs. placebo.

1.1.3 AIM 3: Biomarkers of Neonatal Brain Injury

Aim 3a. To determine whether early high dose Epo decreases the severity of brain injury as evidenced by early neonatal MRI and MR spectroscopy.

Aim 3b. To determine whether early high dose Epo decreases the severity of brain injury as evidenced by serial circulating biomarkers of inflammation and brain injury.

1.2 ENDPOINTS

Primary Efficacy Endpoint

1. *Death or neurodevelopmental impairment at 24 months of age, compared between the two groups.*

Secondary Efficacy Endpoints

2. *Comparison of CP, motor impairment, Bayley III cognitive and learning scores, epilepsy, and behavioral abnormalities at 24 months, compared between the two groups.*

Safety Endpoints

3. *Rates of Epo-related reported adverse events through hospital discharge, compared between the two groups.*
4. *Rates of Epo-related reported adverse events through 24 months, compared between the two groups.*

Exploratory Analyses of Biomarkers of Neonatal Brain Injury

5. *Evaluation of serial circulating biomarkers of inflammation/brain injury, and MR evidence of brain injury obtained during the first week of life, compared between the two groups.*
6. *Evaluation of predictive values of serial circulating biomarkers of inflammation/brain injury, and MR evidence of brain injury obtained during the first week of life, for predicting 24-month neurodevelopmental outcomes.*

1.3 OVERVIEW OF STUDY DESIGN

1.3.1 Definition of Study Day

To ensure study procedures are consistent across sites, the following definition will be used:

Study Day: Study Day 1 is defined as the calendar day on which Intervention 1 (first administration of study drug) occurs. If the study drug is first administered on the calendar day following the day of birth, then the day of birth will be called Study Day 0.

We propose a multicenter, randomized, double-masked, placebo-controlled Phase III clinical trial. We will enroll 500 infants at a minimum of 15, and a maximum of 30 sites. Patients will be randomized to receive either IV Epo 1000 U/kg/dose based on birth weight, or an equal volume of IV normal saline (NS). Study drug will be administered on study days 1, 2, 3, 4, and 7. All enrolled infants will receive standard clinical care including 72 hours of therapeutic hypothermia. The initial neonatal intervention and safety monitoring will begin at time of study consent (prior to 24 hours of age), and will be continued to hospital discharge. Follow-up evaluations will be performed at 4, 8, 12, 18, and 24 months via phone questionnaire, and at 24 months via in person neurodevelopmental examination.

Primary endpoint at age 24 months \pm 56 days (i.e., \pm 2 months) will be determined by presence of death or neurodevelopmental impairment.

Blood samples will be obtained from *all subjects* at 3 time points: baseline, Study Day 2, and Study Day 4. Urine samples will be obtained from *all subjects* at 2 time points: after consent on Study Day 0-1, and after completion of rewarming on Study Day 3-4. We will measure a baseline plasma Epo concentration prior to the administration of the first study drug dose. A subset of 200 patients identified post-hoc after meeting pre-defined criteria for quality of MRI/MRS data will have their samples measured for circulating and urinary biomarkers of brain injury and inflammation. All infants will have a brain MRI and MRS, ideally between 96 and 144 hours post-birth, as part of the standard clinical management of cooled infants. The study neuroradiologists will perform masked centralized reading of these neonatal brain MRI and MRS scans.

Sample Size and Population. We will enroll 500 infants \geq 36 weeks gestational age with ***moderate or severe*** HIE. Eligible subjects (\geq 36 weeks of gestation, admitted to a participating site Neonatal Intensive Care Unit for therapeutic hypothermia) must meet the following criteria from 1 AND 2.

1. **Perinatal depression** = *at least one of the following:*
 - a. *Apgar < 5 at 10 minutes of age, or*
 - b. *Need for resuscitation at 10 minutes (i.e., chest compressions, or positive pressure respiratory support including endotracheal, mask ventilation, or CPAP), or*
 - c. *pH < 7.00 in a cord gas (arterial or venous) or in an infant gas (arterial or venous) obtained at < 60 minutes of age, or*
 - d. *Base deficit $\geq 15 \text{ mmol/L}$ in a cord gas (arterial or venous) or in an infant gas (arterial or venous) obtained at < 60 minutes of age*
2. **Moderate/severe encephalopathy** = *at least 3 of 6 modified Sarnat criteria present between 1-6 hours of age (see Table 4).*^{3,5,26}

Assuming 10% loss of follow-up at 24 months, we will enroll 500 infants, in order to evaluate 450 infants (225 in each arm) at 24 months of age. We plan to apply for additional funding to allow us to follow these children to age 8.

Table 1. Study Procedure Chart

Age	<24 hours	* Entry/ Day 1*	Study Day						Discharge	Months				
			2	3	4	5	6	7		4	8	12	18	24
Informed consent	X													
Randomization	X													
Epo or placebo IV		X	X	X	X				X					
Hypothermia		X												
Blood sample	X		X		X									
Urine sample		X		after rewarming										
MRI/MRS						96-144 hours post-birth								
Sarnat exam	X						X							
Phone interview										X	X	X	X	X
Neurodevelopmental exam														X

* Study Day 1 is defined as the calendar day on which Intervention 1 is administered. If the study drug is administered on the calendar day following the day of birth, then the day of birth will be called Study Day 0.

	Months											
Age	30	36	42	48	54	60	66	72	78	84	90	96
Extended Contact phone calls	X	X	X	X	X	X	X	X	X	X	X	X

Each of the enrolling sites has extensive experience with neonatal clinical research, performs passive or active hypothermia during transport, performs whole body cooling, and has an active neonatal follow-up program.

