6 CLINICAL AND LABORATORY EVALUATIONS

6.1 SCHEDULE OF EVALUATIONS

Table 3. Schedule of Evaluations

Evaluation	Visit Day	Window	Location	Details
Screening	Study Day 0 or 1	Before randomization	NICU	Screening Clinical Assessment (Apgar, resuscitation, acidosis, Modified Sarnat exam, Inclusion/Exclusion assessment)
Therapeutic Hypothermia Begins	Study Day 0 or 1	Begin by <6 hours post-birth	NICU	Begins prior to administration of study drug and at <6 hours of age, continues for 72 hours, per standard of care.
Consent & Enrollment	Study Day 0 or 1	Prior to 24 + 2 hours post-birth	NICU	Informed Consent
Randomization	Study Day 0 or 1	Prior to 24 + 2 hours post-birth	Pharmacy	HEAL Portal
Blood sample (pre-intervention)	Study Day 0 or 1	Before Intervention 1	NICU	1.5 mL blood sample
Urine sample 1	Study Day 0 or 1	1 st void after consent	NICU	1-2 mL urine sample, ideally obtained prior to study drug administration (note: urine may be collected after study drug administration if not available earlier, and in this case, does not require a Protocol Deviation)
Intervention 1 (study drug)*	Study Day 1	Prior to 24 + 2 hours post-birth	NICU	Target time is as soon as possible
Intervention 2 (study drug)	Study Day 2	24 ± 2 hours following Intervention 1	NICU	Target time is same time of day as Intervention 1
Blood sample 2	Study Day 2	24 ± 2 hours following Intervention 1	NICU	1.5 mL blood sample. Target time is same time of day as Intervention 2
Intervention 3 (study drug)	Study Day 3	48 ± 2 hours following Intervention 1	NICU	Target time is same time of day as Intervention 1
Urine sample 2	Study Day 3-4	After rewarming completed, and within 24 hours after rewarming	NICU	1-2 mL urine sample

Evaluation	Visit Day	Window	Location	Details
Intervention 4 (study drug)	Study Day 4	72 ± 2 hours following Intervention 1	NICU	Target time is same time of day as Intervention 1
Blood sample 3	Study Day 4	72 ± 2 hours following Intervention 1	NICU	1.5 mL blood sample. Target time is same time of day as Intervention 4
Brain MRI/MRS (routine clinical care)	Study Day 4-5	Ideally between 96-144 hours post-birth	NICU	After rewarming, and ideally after Intervention 4 has been administered
Clinical assessment	Study Day 5	Anytime this calendar day	NICU	Modified Sarnat exam
Intervention 5 (study drug)	Study Day 7	144 ± 2 hours following Intervention 1	NICU	Target time is same time of day as Intervention 1
EEG Summary	Study Days 1-7	N/A	NICU	Upload EEG reports

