6.2 TIMING OF EVALUATIONS

6.2.1 Pre-Randomization Evaluations – Timing

Screening <24+2 hours post-birth: Screening and pre-entry clinical assessment may occur concurrently. Screening does not involve procedures that are not part of routine patient care. Patients should be screened and evaluated as soon as possible after birth. The Sarnat examination should be performed and recorded between 1-6 hours of age, preferably prior to administration of any sedative drugs. When performed by an outside physician or an individual not trained in the HEAL Sarnat exam, the Sarnat exam should be confirmed by a HEAL study physician (see Section 6.3.2.1).

Consent and Randomization (<24 hours): Consent must occur by 24+2 hours of age (i.e., post-birth). Study entry (i.e. randomization) may occur at any time up to 24+2 hours of age, as long as the first dose of study drug is administered by 24+2 hours (ideally ≤ 24 hours) of age.

Clinical Assessment (<24 hours): For subjects successfully screened, consented, and randomized, a baseline blood sample will be collected prior to giving the first dose of study drug. The 1.5 mL blood sample must be collected within the first 24+2 hours of age, which is the latest time point at which drug administration can begin. A 1-2 mL urine sample will be collected from the first void after consent is obtained. The urine does not need to be collected prior to giving the first dose of study drug. When possible, EEG monitoring will also begin by 24+2 hours of age, as will laboratory monitoring according to the HEAL Clinical Guidelines and institutional guidelines for care of critically ill newborns. We will request placental pathology reports, as available. To facilitate obtaining this data, clinical pathologic examination of the placenta should be performed when possible.

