6.3.5 Plasma and urine biomarkers; baseline Epo measurement

Three blood samples (1.5 mL each) will be collected in EDTA tubes from each enrolled patient over the course of their hospital stay to be used to study circulating biomarkers of inflammation and brain injury. The first blood sample (collected prior to the administration of study drug) will also be used to measure a baseline Epo level. A baseline Epo level may be helpful to determine the chronicity of hypoxic-ischemic stress *in utero*, a potential confounder of the relationship between Epo therapy and 2-year outcome. Additional samples are collected on Study Days 2 and 4.

Samples may be refrigerated for up to 4 hours prior to processing and freezing. As soon as possible after drawing, samples should be spun for 8 min at 2000 G, plasma removed into a separate container, and plasma and pellet stored in labeled tubes at -70°C or below. RNALater will be added to one pellet to preserve RNA for future studies. Please refer to the Laboratory SOP for further details. Plasma Epo concentrations will be measured in duplicate using Meso Scale Discovery (MSD) technology at the UW Laboratory Core.

We will assay blood samples for circulating biomarkers of brain injury and inflammation in a subset of infants (N = 200; 100 treated and 100 control infants with balanced numbers of moderate and severe HIE. These subjects will all have MRI scans that have met pre-defined acceptance criteria). We will assay putative biomarkers of brain injury severity in neonates including: S100B, glial fibrillary acidic protein (GFAP), Tau, neuron-specific enolase (NSE), and ubiquitin C-terminal hydrolase-L1 (UCH-L1). Given the role of inflammation in HIE, we will also measure the following inflammatory markers: interleukin (IL)-1beta (β), IL-6, IL-8, and tumor necrosis factor-alpha (TNF-α). All samples will be run in duplicate using MSD technology in the UW core laboratory. This combination of factors will allow us to evaluate the subject's inflammatory

state over time, provide insight as to the timing and severity of brain injury, and potentially, provide insight as to why some individuals might respond more optimally to Epo.¹²⁴⁻¹²⁷

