9.3.5 Neuroimaging and circulating biomarker analyses

Circulating biomarkers of inflammation and brain injury. Inflammation is thought to play an important role in HIE and CP.¹⁴⁴⁻¹⁴⁷ Biomarkers of inflammation that we measure include: interleukin (IL)-1 β , IL-6 and IL-8 and TNF- α . Putative biomarkers of brain injury in neonatal HIE include: glial fibrillary acidic protein (GFAP), ubiquitin C-terminal hydrolase-L1 (UCH-L1), S100B, Tau, and neuron-specific enolase (NSE). We will select a random subset of 200 subjects (100 treated and 100 controls with each group, for example, including both moderate and severe HIE) to measure circulating biomarkers of inflammation and brain injury. We will collect 3 plasma samples from each infant at the following time points based on hour of age: < 24 hours; Study Day 2; Study Day 4. Our analysis will focus on time-specific comparisons of the mean biomarker measure across treatment groups using appropriate regression methods while controlling for site and HIE severity. In addition, we will conduct longitudinal analysis using linear mixed models¹⁴⁸ that permit an omnibus test across all four measurement times, and allow inference on differential rates of change across treatment groups.

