## 5.7 Circulating Biomarkers

Inflammation is thought to play an important role in HIE and CP. Biomarkers of inflammation that we measure include: interleukin (IL)-1 $\beta$ , IL-6 and IL-8 and TNF- $\alpha$ . Putative biomarkers of brain injury in neonatal HIE include: glial fibrillary acidic protein (GFAP), ubiquitin C-terminal hydrolase-L1 (UCH-L1), S100B, Tau, and neuron-specific enolase (NSE). We will select a random subset of 200 subjects (100 treated and 100 controls with each group, for example, including both moderate and severe HIE) to measure circulating biomarkers of inflammation and brain injury. We will collect 3 plasma samples from each infant at the following time points based on hour of age: < 24 hours; Study Day 2; Study Day 4. Our analysis will focus on time-specific comparisons of the mean biomarker measure across treatment

groups using appropriate regression methods while controlling for site and HIE severity. In addition, we will conduct longitudinal analysis using linear mixed models that permit an omnibus test across all four measurement times and allow inference on differential rates of change across treatment groups.

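### The 200 biomarker infants are chosen on MRI acceptability in the Protocol's design sections but called a random subset in the analysis sections; under the MRI rule the exploratory Epo-placebo comparison conditions on a post-randomisation event

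*Protocol*

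**What the plan says.** Four places describe the same 200 infants, and they fall into two pairs.

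- **MRI-selected.** The design overview in Protocol 1.3.1 has "A subset of 200 patients identified post-hoc after meeting pre-defined criteria for quality of MRI/MRS data". Protocol 6.3.5 states "These subjects will all have MRI scans that have met pre-defined acceptance criteria" and does not mention random selection.
- **Random.** Protocol 9.3.5 states "We will select a random subset of 200 subjects", and SAP 5.7 uses the same words. Neither mentions MRI.

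The severity mix differs too. Protocol 6.3.5 asks for "100 treated and 100 control infants with balanced numbers of moderate and severe HIE". Protocol 9.3.5 and SAP 5.7 only give, as an example, that each arm would contain both severities.

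The sample serves a between-arm question. Aim 3b asks whether Epo reduces brain injury "as evidenced by serial circulating biomarkers of inflammation and brain injury", and SAP 5.7 plans "time-specific comparisons of the mean biomarker measure across treatment" groups, controlling for site and HIE severity.

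On timing, Protocol 6.2.1 says randomisation "may occur at any time up to 24+2 hours of age". The schedule in Protocol 6.1 places the MRI ideally at 96-144 hours, "After rewarming, and ideally after Intervention 4 has been administered".

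**The concern.** Whether an infant has an acceptable scan is known only after randomisation, and usually after most of the study drug has been given. Selecting on it means that baseline and Study Day 2 samples are used or set aside according to what happened later. The infants lost are those who die or move to comfort care before any scan, and those whose scan fails the quality criteria. At least the first group is likely to include infants with high injury markers.

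If Epo affects who reaches an acceptable scan, the arms among selected infants are no longer comparable by design. Adjustment for site and baseline HIE severity does not repair this, because the selection acts on later events. Separately, a programmer following the SAP and one following Protocol 6.3.5 would draw different samples.

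**Working it through.** **1. The plan's own figures.** Protocol 9.4.3 and SAP 7.3 state 80% power for 0.4 SD with 200 infants. The alpha is not given; I assume two-sided 0.05. Power = Φ(0.4/√(2/100) − 1.96) = Φ(0.868) = 80.7%, so the figure reproduces. Protocol 9.4.4 and SAP 7.4 state 91 per group for 0.5 SD at alpha 0.0125; the normal formula gives 90 and the t-test 90.8, so that reproduces as well. The sample size is not in question. What is in question is who the 200 are.

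**2. Can the four places be reconciled?** One can read them together as a random draw from infants with acceptable scans. That settles the wording on MRI. It does not settle the severity mix, and it leaves eligibility dependent on a scan done days after the first dose. Only a draw from all dosed infants removes the conditioning.

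**3. Who is excluded under the MRI rule?** Protocol 1.3.1 and 6.3.5 set a quality condition without a time limit. Protocol 6.3.6 lets an infant who is unstable in the window be scanned later and does not count that as a deviation. Temporary instability therefore need not exclude. What remains is death or comfort care before any scan (Protocol 6.2.2 foresees comfort care without prior head imaging) and scans that fail the criteria.

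**4. Illustration of size.** The documents give no scan-failure rate by arm. My assumptions: latent severity is standard normal, the excluded fraction q is its worst tail, the marker correlates with severity at ρ, and each arm is still filled to 100. The mean severity of those kept is m(q) = −φ(c)/(1−q), with c = Φ⁻¹(1−q).

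*No true effect* (bias = ρ × difference in m):

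| Control q | Epo q | m control | m Epo | Bias, ρ = 0.3 to 1.0 |
|---|---|---|---|---|
| 14% | 14% | −0.259 | −0.259 | 0 |
| 14% | 12% | −0.259 | −0.227 | 0.009 to 0.031 SD |
| 20% | 10% | −0.350 | −0.195 | 0.046 to 0.155 SD |

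The 14% and 12% are the death rates that Protocol 9.4.1 builds into the 24-month composite; using them here assumes that every death precedes the scan. The 20% and 10% are mine, as a stress case; there the type I error at nominal 5% is about 6% to 20%. In the unequal rows Epo looks worse than it is, because controls lose more of their severe tail. If Epo lost more, the sign would reverse.

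*True effect of 0.4 SD, ρ = 1, one severity threshold for both arms:*

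| Control q | Epo q | Mean kept, control | Mean kept, Epo | Observed difference | Power, SD 1 | Power, truncated SD |
|---|---|---|---|---|---|---|
| 7% | 3.0% | −0.144 | −0.471 | 0.33 SD | 64% | 73% |
| 14% | 6.9% | −0.259 | −0.543 | 0.28 SD | 52% | 67% |

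The Epo mean is −0.4 − φ(c+0.4)/Φ(c+0.4). The comparator is the 80.7% in step 1.

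**The case against.** The case for leaving this alone is substantial.

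- **The analysis is exploratory.** Protocol 1.2 and SAP section 4 both list it so. This stands: no primary, secondary or safety conclusion depends on it.
- **The texts may be compatible.** A random draw among scanned infants fits most of the wording. This stands for the wording only (step 2).
- **The bias may be negligible.** With similar losses in the two arms and no effect there is none, and at 14% versus 12% it is at most about 0.03 SD against a planned 0.4 SD. This stands; the larger figures need inputs that the documents do not give.
- **The plan already has safeguards.** Protocol 9.3.6.1 plans inverse-probability weighting for attrition and non-participation, and SAP 5.8 compares the imaging sample with the full trial. Neither is tied to selection of the biomarker subset, and SAP 6.3 drops the weighting. This stands only in part.
- **Infants with both data types are needed.** The combined MR and plasma prediction model (Protocol 9.3.3, SAP 5.4) requires them. That is a good reason for the MRI rule in that model, but not in the treatment comparison.

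A reader might go further and infer that 10-14% of each arm is selectively removed, or that randomisation is broken. The documents support neither. The 12-14% is death counted in a 24-month endpoint, not death before a scan. The 10% is a missing-data allowance used for imaging power. No difference between arms in reaching an acceptable scan is shown. Nor can one infer that every infant too unstable for a scan in the window is lost (step 3).

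**Conclusion.** The inconsistency is real, and it matters for one exploratory comparison. If Protocol 1.3.1 and 6.3.5 are followed, the Aim 3b contrast is among infants selected on a post-randomisation event. If the random-subset text governs and means all dosed infants, it is not.

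The size cannot be estimated from the documents. The illustrations run from about 0.01-0.03 SD (14% versus 12% excluded, no effect) to shrinkage of a true 0.4 SD effect to 0.33-0.28 SD in a deliberately unfavourable case. All rest on the assumption that the excluded infants are the most severe tail. The more plausible harm is a diluted or uninterpretable biomarker result rather than a large false signal. The primary endpoint is unaffected.

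**What to change.** State one selection rule in Protocol 1.3.1, 6.3.5 and 9.3.5 and in SAP 5.7.

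- **Treatment comparison:** draw the 200 at random within arm and HIE severity from all mITT infants with a pre-dose sample, regardless of MRI. If severe HIE is over-sampled, use design weights so that the overall estimate reflects the trial's severity mix.
- **Prediction models combining MR and plasma markers:** apply the MRI acceptance criteria here only.
- **Later samples:** report missing Study Day 2 and Day 4 samples by arm and reason. Death before Day 4 leaves survivor selection at that time point under any sampling rule.
- **If MRI-based selection has already been made:** report MRI-acceptable rates and reasons for exclusion by arm, extend the SAP 5.8 comparison to this subset, and add an inverse-probability-weighted sensitivity analysis.

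The cost is a change of sampling rule, not of size: still 200 infants, with up to three samples each, and still 80.7% power for 0.4 SD when samples are complete. The downside is somewhat fewer infants with paired MRI and biomarker data. If the plan's 10% missing-imaging allowance applied, that would be about 0.10 × 200 = 20 infants.
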